### Eligibility Criteria

Inclusion Criteria:

- 1) DSM-5 diagnosis of an Alcohol Use Disorder (AUD)
- 2) Adults ages 21 to 65 years old
- 3) Expressed desire to stop drinking alcohol completely or to reduce alcohol consumption
- 4) Reported drinking an average of at least 14 standard drinks per week for males, or 7 for females occurring over a 28-consecutive day period during the 90 day-long time window that preceded the screening session
- 5) Must be willing to discontinue psychotherapy for substance use disorder (except A.A. session attendance)

Exclusion Criteria (exclusion criteria are the specific criteria which would disqualify an individual from participating in the study, not simply the opposite of the inclusion criteria):

Exclusion from Recruitment:

- 1) Bipolar disorder, schizophrenia, current bulimia/anorexia, dementia, or other substance use disorder, with the exception of nicotine, marijuana, and caffeine.
- 2) Clear and current suicidal risk. Subjects who are determined by either the medical team or PI to be at moderate to high risk of suicide (as evidenced by reports of the following: persistent thoughts about how one might kill themselves, intentions of acting on thoughts of killing themselves, making plans to kill themselves, making preparations to kill themselves, a suicide attempt in the past year, or 2 or more hospitalizations due to depression within the past 5 years) will be excluded from recruitment.
- 3) Significant medical problem (e.g. uncontrolled diabetes, cancer, uncontrolled hypertension) or neurological conditions (e.g., seizures, dementia, PD) that in a clinical context would require prioritization for immediate treatment or simultaneous treatment that could interact with the study treatment in unknown ways.

4) Medical contraindication to the use of ZON, as indicated by the FDA Zonisamide medication guide. These include history of significant renal disease or current renal impairment (as indicated by creatinine levels greater than 2.0 mg per dL in females and 2.5 mg per dL in males), kidney stones, liver problems (as indicated by AST/ALT outside of normal limits), and evidence of metabolic acidosis (as indicated by serum or plasma bicarbonate < 22 mmol/L)

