#### Exclusion from Participating in the Active Treatment:

12) Reduction in the mean number of drinks consumed per week by 50% or more between the phone screen and the in-person screening or report of average drinks per day falling within safe levels of alcohol consumption (i.e. 2 drinks/day for males and 1 drink/day for females by the HHS standard) two weeks prior to screening.

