- If the participant's BAC is greater than 0.00% before signing the informed consent, he/she would have to reschedule the screening, which can be a few hours later or another day. If asked to reschedule, the participant will be asked not to drive home and

to make other transportation arrangements. If no one is available to take the participant home, a study staff member may call a taxi or car service. CARD will cover transportation expenses in this circumstance.

After the participant signs the consent form, they will receive a copy of it. Prior to conducting the first neuroimaging procedure at BU CILSE, study staff will also review the imaging procedures with the participant.

The consent form also specifies that data from the present study (#4299) will be combined with data from the supplemental study (#4890E) if participants sign consent for both studies.

For all other study sessions, participants with BAC levels greater than 0.02% will be asked to remain at the center until their levels reach below 0.02, or reschedule if necessary. Again, if a participant is drunk and is asked to reschedule the appointment, the participant will be asked not to drive home and to make other transportation arrangements. If no one is available to take the participant home, a study staff member may call a taxi or car service.

The first study session will be scheduled within 4-weeks after their in-clinic screening. If the one-month window expires before the participant can come in to CARD again, then the in-clinic screening session will have to be repeated to assess the participant's eligibility for the study.

Participants who meet eligibility for the study following the telephone and in-clinic screening will be notified of their eligibility to participate in our study via telephone by our study staff. Potential participants will be told that they can take up to two weeks to notify us of whether they would like to participate in this study or whether they need more time to decide. Potential participants who need more time to decide, will be told that they can contact us again whenever they're ready, as long as the study hasn't ended. However, as noted above, if there has been more than one-month between the screening and the participant's first treatment session, we may have to repeat the screening process to ensure eligibility for enrollment at that point in time.

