#### Data Analysis

1. Demonstrate that ZON will attenuate changes resulting from performance on alcohol-word and negative-word Stroop tasks in the activity of frontal-parietal and midbrain regions and the connectivity to networks associated with these regions in AUD subjects. Our working hypothesis is that midbrain activity will be lower in ZON treated subjects than in placebo subjects following performance on alcohol and negative emotion Stroop task, which will occur in association with enhanced mid-brain-frontal connectivity and increased synchrony.

Fixed effects models will be used to analyze data for brain activation in regions of interest, with treatment group as a between group factor and Stroop task type and order of stimuli presentation will be within subject factors. Regions of interest will include parahippocampal gyri, midbrain substantia nigra and red nucleus, dorso-lateral prefrontal cortex, and cerebellum.

Connectivity will be assessed using the Free Surfer analysis described below. Seeds will be used for the dorsolateral prefrontal cortex and the midbrain (substantia nigra) following Muller-Oehring et al. (2013).

2. Demonstrate that ZON administration attenuates the enhanced regional brain activity and craving- induced by exposure to alcohol related cues in AUD subjects. Our hypothesis is that exposure to alcohol-related cues will increase brain activity in select limbic and prefrontal areas to a lesser degree in ZON as compared to placebo treated AUD subjects.

Fixed effects models will be used to analyze data for brain activation in regions of interest, with treatment group as a between group factor and stimulus type and order of stimuli presentation was within subject factors. Regions of interest, based on the meta-analysis of Schacht et al. (2013), will include the ventral striatum, medial prefrontal cortex, and the anterior cingulate cortex.

3. Demonstrate that the ZON induced changes in brain activity are predictive of reduced ethanol consumption.

Logistic regression analysis will be used to evaluate zonisamide-induced decreases in the BOLD response in the ventral striatum and the medial prefrontal cortex as predictors of complete abstinence or reduction to safe drinking levels (defined as consumption of no more than more than 2 standard drinks per day) during study weeks 10 to 12.

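### Aim 3 uses one limit of 2 drinks a day for both sexes and no comparison with the participant's own baseline, so some women count as having reduced their drinking with no change

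*Combined protocol and SAP*

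**What the plan says.** Aim 3 in Section L (Data Analysis) sets out a logistic regression with BOLD decreases in the ventral striatum and medial prefrontal cortex as predictors. The binary outcome is "complete abstinence or reduction to safe drinking levels (defined as consumption of no more than more than 2 standard drinks per day", assessed "during study weeks 10 to 12". There is no separate figure for women and no minimum fall. The text does not say whether the limit is a mean or a ceiling for each day.

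Two entry rules in Section I bear on this:

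- Inclusion 4: "Reported drinking an average of at least 14 standard drinks per week for males, or 7 for females occurring over a 28-consecutive day period". The 28 days may fall anywhere in the 90 days before screening.
- Exclusion 12 bars from active treatment anyone with a "report of average drinks per day falling within safe levels of alcohol consumption (i.e. 2 drinks/day for males and 1 drink/day for females") in the "two weeks prior to screening". It also bars anyone with a "Reduction in the mean number of drinks consumed per week by 50% or more between the phone screen and the in-person screening".

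Section K adds a possible gap: "The first study session will be scheduled within 4-weeks after their in-clinic screening". Exclusion 12 refers only to the time up to screening.

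**The concern.** The outcome is meant to capture reduced drinking, but as defined it captures only the level reached. The level is 2 a day for everyone, whereas the protocol's own safe level for women, used at entry, is 1 a day. A woman can therefore be eligible because she drinks above the protocol's safe level, stay exactly where she is, and be recorded as having come down to a safe level.

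Aim 3 is the link between the imaging aims and the drinking outcome. If some successes are people whose drinking did not change, the responder group mixes reducers with women who entered at a low level. Part of what the regression then predicts is entry level and sex rather than change. The target sex ratio is 55:45, so women are not a small subgroup.

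**Working it through.** **Plan's own figure.** There is none to reproduce. The Power Analysis paragraph gives no responder rate and no power for the Aim 3 regression.

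**Putting the limits on one scale (average reading).**

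- Aim 3 limit: 2 × 7 = 14 drinks a week, both sexes.
- Inclusion 4 floor: men 14/7 = 2.0 a day; women 7/7 = 1.0 a day.
- Exclusion 12: over the last 14 days before screening, men must exceed 2 × 14 = 28 drinks and women 1 × 14 = 14 drinks.

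**Women.** Take a steady 12 drinks a week: 12/7 = 1.71 a day. This is at least 7 a week, so inclusion 4 is met. It is above 1 a day, so exclusion 12 does not apply. It is not above 2 a day, so the Aim 3 limit is met before the first dose. The same holds for any steady level above 7 and up to 14 a week. No assumption is needed beyond the average reading.

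**Men.** A man who drinks 30 in the last fortnight averages 30/14 = 2.14 a day (15 a week) and passes exclusion 12. If he drinks 42 in weeks 10 to 12, that is 42/21 = 2.0 a day, and he is a responder. His fall is (15 − 14)/15 = 7%. If he drank 26 in the fortnight before that, his 28-day mean was (26 + 30)/4 = 14 a week, so he has not fallen at all from his 28-day average. He has still fallen from his last two weeks.

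**How often, with no change in usual level.** The documents give neither a baseline distribution nor within-person variability, so these inputs are assumed. Weekly level varies independently with CV 0.2 or 0.4, and daily counts are negative binomial with k = 1 or 0.5 respectively. Each setting has 200,000 simulated participants. Both entry rules are applied, with inclusion 4 taken on the last 28 days. Each cell gives the results for the two variability settings.

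| Sex, usual drinks/day | Already at or below 2/day on 28-day baseline | At or below 2/day in weeks 10–12 |
|---|---|---|
| Women 1.5 | 86.7%, 75.2% | 87.1%, 81.0% |
| Women 2.0 | 51.7%, 49.3% | 55.2%, 57.5% |
| Women 3 | 6.9%, 15.8% | 11.0%, 22.9% |
| Women 4 | 0.5%, 4.6% | 1.6%, 8.5% |
| Men 2.2 | 2.7%, 2.3% | 42.6%, 48.3% |
| Men 2.5 | 1.4%, 1.5% | 26.7%, 37.2% |
| Men 3 | 0.5%, 0.9% | 11.1%, 22.9% |
| Men 4 | 0.0%, 0.2% | 1.6%, 8.5% |
| Men 6 | 0.0%, 0.0% | 0.0%, 1.3% |

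The first column separates the sexes. Women near their entry floor mostly meet the definition at baseline; men almost never do. Men near the limit reach it by fluctuation.

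**Whole sample.** A second no-change simulation assumed enrolled medians of 22–37 drinks a week for men and 13–24 for women, between-person log SD 0.6, and weekly log-level SD 0.3–0.5 with autocorrelation 0.7. Response as written was 6–33% in men and 21–61% in women. At 55:45 the overall rate is 0.55 × 6 + 0.45 × 21 = 13% to 0.55 × 33 + 0.45 × 61 = 46%. With 1 a day for women and nothing else changed, it was 5–29%. Read as a cap on every day, the rate in men was 0.1–4%.

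**The case against.** The strongest reply is that the average reading is not established. Exclusion 12 says average; Aim 3 does not. Under Aim 4, heavy drinking is defined by a number of drinks per day and feeds a percentage of days, so there the same form of words is a single-day threshold. If Aim 3 means a daily cap, the rate in men falls to 0.1–4%. A woman at 12 a week would qualify only if she never exceeded 2 on any day (five days of 2 and two of 1, for example). This stands as a reason to state which is meant. It does not settle the sex-neutral limit, which departs from exclusion 12 on either reading.

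A second reply is that the outcome is worded as a reduction, so a fall is implied. The only operational content is the 2-a-day figure, and the word alone would accept a fall of any size.

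A reader might go further and infer that men also enter at the response limit, need no fall, and so become responders through ordinary fluctuation alone. The documents do not support that. Exclusion 12 keeps out men averaging 2 a day or less in the two weeks before screening, so meeting the limit needs some fall from that level. Chance crossing is common only near the limit, and it is rare at 4 a day and above.

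Nor has a false-positive BOLD association been shown. Misclassification unrelated to BOLD mainly adds noise. Aim 4 analyses drinking measures with baseline covariates and is untouched.

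**Conclusion.** The concern holds for women and, more weakly, for men. On the average reading, women drinking more than 1 and up to 2 a day satisfy both entry rules and the Aim 3 response definition at the same time, so they can be scored as reduced without any change. For men the limit coincides with the inclusion 4 floor, but exclusion 12 forces some fall from the last two weeks before screening, possibly as little as 7%.

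The contradiction between the 2-a-day limit in Aim 3 and the 1-a-day level for women in exclusion 12 is plain from the text. The number of participants affected is not: it depends on the unknown baseline distribution and variability, and on the average reading. If dropout is 20% in each sex, 45 × 0.8 = 36 of the 80 participants at week 12 would be women, and only those who entered at low levels are exposed to the no-change problem. This is a flaw in what the outcome means, worth correcting before analysis. It is not a threat to the trial's drinking-efficacy comparison.

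**What to change.** Replace the Aim 3 outcome sentence with a definition along these lines. Response is abstinence throughout weeks 10 to 12, or a mean of TLFB drinks per day over those weeks that is both (a) no higher than the safe level in exclusion 12 (2 for men, 1 for women) and (b) lower than the participant's own mean over a stated pre-treatment window. A fixed window ending at the first dose is preferable to the qualifying 28 days, which may be an unusually high stretch.

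Both conditions are needed. Changing the women's limit alone would only make it equal their entry floor, as it already is for men. Condition (b) still lets a small chance fall count. Report two sensitivity analyses: the present 2-a-day definition, and a version requiring at least a 50% fall from baseline. The 50% figure comes from the pre-treatment screen in exclusion 12 and is not an established response criterion, so it should not be primary.

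The cost is one sentence. Table 1 already schedules the TLFB at screening, in week 1 before treatment and weekly thereafter. There will be somewhat fewer responders among women. For the 50% version, a simulation with a real average reduction (mean log change −0.5 or −0.7) gave 32–46% responders against 47–64% as written, with power for the BOLD term at n = 80 changing by −1 to +4 points. The gain is therefore in what the outcome means, not in power.

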**III. Alcohol Use Related Assessments**

- A) **Alcohol Dependence Scale (ADS)** - Alcohol dependence will be assessed using the ADS. This 25-item scale has an internal consistency reliability estimate of 0.92 (Skinner & Allen 1982).
- B) **Beck Depression Inventory II (BDI-II)** - BDI II will be used to detect depression in participants. The 21-item assessment encompasses all DSM-based depressive symptoms.

The BDI-II has been found to be reliable among medical samples (and it has demonstrated stability among psychiatric ( $r = 0.92$ ) and student ( $r = 0.93$ ) samples (Beck et al., 1996).

- C) **Alcohol Timeline Follow-Back (TLFB)** - TLFB will be used to estimate participants' daily drinking. In this assessment, participants are presented with a calendar and asked to provide retrospective estimates of their daily alcohol consumption over a specified time period. It takes approximately 25-30 minutes to gather 12 months of data, and approximately 10 minutes to gather 90 days of data. The TLFB has a high test-retest reliability and correlates with other established measures of alcohol use (Sobell & Sobell, 1992).
- D) **Clinical Institute Withdrawal Assessment for Alcohol Scale, Revised (CIWA-A)** - CIWA-A will be used to evaluate the severity of withdrawal symptoms. This 10-item scale, shortened from the 15-item CIWA-A scale, retains significant accuracy when compared to the original CIWA-A ( $r=0.99$ ; Sullivan, Sykora, Schneiderman, Naranjo & Sellers, 1989).
- E) **Obsessive Compulsive Drinking Scale (OCDS)** - OCDS will be used to assess alcohol craving and the urge to drink. The OCDS is a 14-item self-report questionnaire developed based on the Yale-Brown Obsessive Compulsive Scale, an interview-based rating scale. It takes approximately 5-10 minutes to complete. The OCDS is significantly correlated with independent measures of alcohol craving and with the amount of alcohol consumed, and has a positive relationship with independent measures of the severity of alcoholism (Anton, Moak, & Latham, 1995).
- F) **Alcohol Use Questionnaire (AUQ)** - AUQ will be used to assess alcohol craving and the urge to drink. The AUQ is an 8-item self-report questionnaire, in which participants rate their agreement or disagreement to statements on a Likert-type scale. AUQ scores are strongly correlated to the severity of alcohol dependence and to cognitive preoccupation with alcohol, and decline with prolonged abstinence from alcohol (Bohn, Krahn, Staehler, 1995)

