4. Replicate the finding that ZON will reduce alcohol consumption in AUD subjects. Our working hypothesis is that the drinks consumed per day and percent days drinking will be significantly lower in AUD subjects receiving ZON than in those treated with placebo.

Drinking measures derived from the TLFB data will include the percent days drinking, the number of drinks consumed per day, and the percent days heavy drinking. Heavy drinking will be defined as 4 or more drinks per day for women and 5 or more drinks per day for men.

Alcohol consumption measures will be analyzed using repeated measures mixed models analysis using SAS PROC MIXED (ver 9.3, SAS Institute, Cary, NC) with baseline values for these measures used as covariates. Comparisons will be made for data obtained for the 12 week treatment period for the two conditions.

5. Demonstrate that ZON administration will reduce impulsive and risk taking behaviors. Our working hypothesis is that the ZON will decrease risk taking behavior as assessed using the Rogers Risk Task and the Balloon Analog Risk Task and impulsivity as measured using the Go/NoGo and the Continuous Performance Test (CPT).

Repeated measures mixed models analysis will be used to analyze data obtained for pre-randomization and week 12 data for the Rogers Risk Task, the Balloon Analog Risk Task, the Go/NoGoTask, the CPT, and Go/No Go. Model generated group least square means values for week 12 will be compared using student t-tests.

[name] will provide statistical consultation. He will not have access to identifiable information and will not have any contact with study participants.

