CONN creates subject-specific ROI files and registers them to the subject space. 99 ROIs will be used as the seeds of interest for whole-brain subject-specific ROI-ROI connectivity analyses.

**Power Analysis:** Power analysis for drinks consumed per day during the last three weeks of treatment were determined using data for the placebo and zonisamide groups from our previous study (Knapp et al., 2015). A power value of 0.9 was found for a group size of 40, with alpha=0.05, and with an effect size of 0.74. In our previous study of ZON approximately 20% of subjects dropped out before week 12 of the study. Consequently, we will randomize 50 subjects per group to reach a target of 40 subjects in week 12 of the present study. Based on data reported by Rubio et al. (2009) for errors of commission on the CPT, a measure of impulsivity, a power value of 0.97 would be obtained for an alpha value of 0.05 for a group size of 40. Based on the findings of Myrick et al., (2008) for the difference between the activation of the ventral striatum for placebo and naltrexone groups a power of 0.88 was seen for an effect size of 0.7 for a group size of 40.

**Safety Analysis:** For safety, subjects will be assessed as having had any serious adverse event during the treatment period or not, and additional analyses will be done by separate types of adverse events. Tolerability will be assessed as a subject being able to continue on the study drug for the entire study duration without requiring discontinuation. The safety and tolerability of the study medications will be first assessed using contingency tables and chi-square tests. Fisher's exact test will be employed for rare adverse events. The chi-square analysis will be followed by logistic regression analyses, adjusting for the stratification factor. Time to drug discontinuation for serious adverse events and time to withdrawal from the study for any reason will be assessed using Kaplan-Meier survival curves and compared between study treatments using the log rank test. Poisson regression will be used to evaluate the rate of serious adverse events by arm stratified by the time periods of dosage escalation, dosage maintenance, and dosage taper.

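### Aim 3 scores safe drinking at 2 drinks a day for everyone, although the protocol's own safe level for women is 1 a day

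*Combined protocol and SAP*

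**What the plan says.** Section L, Data Analysis, item 3 (Aim 3) has the goal "Demonstrate that the ZON induced changes in brain activity are predictive of reduced ethanol consumption". Its method is a logistic regression with decreases in BOLD response as predictors. The outcome is complete abstinence or, alternatively, "reduction to safe drinking levels (defined as consumption of no more than more than 2 standard drinks per day) during study weeks 10 to 12". No separate value is given for women.

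Section I, exclusion criterion 12, keeps out of active treatment anyone with a "report of average drinks per day falling within safe levels of alcohol consumption (i.e. 2 drinks/day for males and 1 drink/day for females" in the two weeks before screening, and attributes those levels to an HHS standard.

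The other drinking thresholds also differ by sex:

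- Inclusion criterion 4: "Reported drinking an average of at least 14 standard drinks per week for males, or 7 for females", over a 28-day period in the 90 days before screening.
- Data Analysis, item 4 (Aim 4): "Heavy drinking will be defined as 4 or more drinks per day for women and 5 or more drinks per day for men".

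No section gives a reason for a common limit in Aim 3.

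**The concern.** Two parts of one protocol state what counts as safe drinking, and for women they disagree by a factor of two. Followed as written, the plan would report some women as having reached safe drinking at an intake that its own eligibility rule treats as not safe.

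There is a further difficulty because Aim 3 is about reduced consumption. Some women can enter the trial already at the Aim 3 level, and no minimum change from baseline is stated. For them, success need not reflect any effect on drinking. The word reduction may imply some fall, but no amount is given, so it cannot be scored.

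The sentence is also incomplete. It does not say whether 2 a day is an average over weeks 10 to 12 or a limit on each day, and its wording repeats two words.

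**Working it through.** The plan gives no power, expected success rate or other figure for the Aim 3 regression, so there is no stated figure to reproduce. The check compares the definitions and then sizes the group they could affect.

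**1. The definitions on one scale (drinks a day)**

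| Place | Men | Women |
|---|---|---|
| Exclusion criterion 12, safe level | 2 | 1 |
| Inclusion criterion 4, entry floor | 14/7 = 2 | 7/7 = 1 |
| Aim 3, safe level in weeks 10 to 12 | 2 | 2 |

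The male values agree in all three rows. The female value in Aim 3 is 2/1 = 2 times the protocol's own safe level. Per week it is 2 × 7 = 14 drinks, which is 14/7 = 2 times the female entry floor.

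**2. Who is scored differently**

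- On either reading, a woman taking exactly 2 drinks every day in weeks 10 to 12 is within the Aim 3 level and above the level in criterion 12.
- If the limit is an average, the women rescored under a limit of 1 are those averaging above 1 and up to 2 a day.
- If the limit applies to every day, they are those with at least one day above 1 and none above 2.

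**3. Overlap at entry**

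Take a woman drinking a steady 1.5 a day, or 1.5 × 7 = 10.5 a week. She meets the entry floor of 7 and is above the safe level of 1, so neither drinking criterion keeps her out. On the average reading she already satisfies the Aim 3 limit of 2. On the every-day reading the same is true only of women in this band who have no day above 2.

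For men, criterion 12 empties this overlap on the average reading, but only in the two weeks before screening. Section K says "The first study session will be scheduled within 4-weeks after their in-clinic screening", so a man's drinking could fall to 2 or below before treatment starts.

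**4. Planned number of women**

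Section I gives a male:female target of 55:45. The Power Analysis paragraph of Section L says "we will randomize 50 subjects per group to reach a target of 40 subjects in week 12". Assume equal dropout by sex and two usable scans for each person:

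- Both arms: 0.45 × 80 = 36 women.
- Zonisamide arm only: 0.45 × 40 = 18 women.

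Both are shown because the predictor is described as a zonisamide-induced change, which leaves open whether placebo subjects enter the model.

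**5. Effect on the success rate**

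The share of women who would be rescored is not in the documents. The range below is an assumption.

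| Share of women rescored | Of 36 | Of 18 | Fall in overall success rate (n/80 or n/40) |
|---|---|---|---|
| 5% | 1.8 | 0.9 | 2.25 points |
| 10% | 3.6 | 1.8 | 4.5 points |
| 20% | 7.2 | 3.6 | 9.0 points |
| 30% | 10.8 | 5.4 | 13.5 points |

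**6. What is not affected**

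The stated power of 0.9 for drinks a day (40 per group, effect size 0.74, alpha 0.05) reproduces at 0.911 by the normal approximation and 0.905 by the two-sided t-test. The dropout allowance reproduces as 40/(1 − 0.20) = 50 per group. Neither uses the Aim 3 definition.

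**The case against.** A screening rule and an outcome measured in weeks 10 to 12 can differ by design, and the effect is limited. It touches one mechanistic regression with no stated power. Gender is a factor in the adaptive randomization, so any sex-specific scoring difference should be roughly balanced between arms. The 5% to 30% range has no source in the documents, and the true share could be zero. The counts of 36 and 18 are also upper limits: they need two usable scans each, and the Covid-19 paragraph of Section L, which moves study sessions to video, does not say whether scanning continued.

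Most of this stands as a limit on size. The percentage-point range is conditional on the assumed share, and no direction or size of bias in the BOLD association has been shown. Balance between arms does not protect that association, because the regression relates brain response to outcome and no sex term is listed. Intent does not remove the conflict either: both places claim to state the safe level, and no reason for the difference is given.

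**Conclusion.** The concern holds. Aim 3 and exclusion criterion 12 give different safe levels for women, 2 and 1 drinks a day, without explanation. This rests on the text alone and needs no assumption.

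How much it matters is uncertain. With at most 36 women of 80 at week 12 (18 of 40 if only the zonisamide arm is used) and an assumed 5% to 30% rescored, the Aim 3 success rate would be about 2.3 to 13.5 points lower. The rate could not rise, because the limit for women only becomes stricter. The correction should be made before analysis. The open choice between an average and an every-day limit is secondary, but it affects men as well and should be settled at the same time.

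**What to change.** In Data Analysis, item 3, define the weeks 10 to 12 outcome by the levels already in exclusion criterion 12: no more than 2 standard drinks a day for men and no more than 1 for women. State whether this is an average over the period or a limit on every day. An average would match criterion 12, but the present text does not show which was meant. Remove the repeated words. If a common limit of 2 was intended, the plan needs to give the reason and stop describing that level as safe for women.

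The cost is one or two sentences. In the TLFB, participants are "asked to provide retrospective estimates of their daily alcohol consumption over a specified time period", so either reading can be scored without new data. The success rate in women may fall, which would leave the regression with fewer successes. The Covid-19 paragraph shows that the trial was already running, so the change should be dated and made before unblinding, with the present limit of 2 for everyone kept as a sensitivity analysis.
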